## 6 Introduction

Stryker introduced multiple devices to treat deformity in the neuropathic patient (lack of sensation with the 10 gram Semmes Weinstein monofilament) population. All of the devices have been cleared by the FDA. See below for the list of devices, dates of clearance, and FDA 510K numbers.

Device Name	Date of Clearance	510K Number
HOFFMANN® LRF SYSTEM	01Feb2021	K203568
SALVATION™ EXTERNAL FIXATION SYSTEM	06Jun2018	K180832
SALVATION™ FUSION BOLTS AND BEAMS	21Mar2014	K140741
SALVATION™ 2 MIDFOOT NAIL	11Jul2018	K180024
SALVATION™ 3DI PLATING SYSTEM	22May2014	K140792
SALVATION™ OSTEOPENIC SCREW	14May2014	K140408
T2® ICF SYSTEM	20Mar2020	K193366
VALOR™ ANKLE FUSION NAIL	22Oct2014	K142602

Table 6.1 Study Device FDA 510K Clearance Information

The primary outcome measure of this study will compare the pooled cumulative 3-year amputation rate derived from a Kaplan-Meier survival analysis to a performance goal derived from a literature-based source. Descriptive analyses will then compare survival curves in patients for specific devices over the entire 5-year follow-up period. Secondary endpoints include improvements in patient-reported pain, function, and social interaction for quality of life from pre-op through each annual visit as assessed by the EQ-5D-5L and the FAAM and its component scores. As well as investigator assessment of the implant including radiographic assessment of deformity correction, and fusion/consolidation time through 1 Year

The outcome measures collected in this study will be analyzed and reported as required for local, regional, and country requirements (i.e., regulatory authorities and notified bodies).

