## 9.4 WITHDRAWAL CRITERIA

If, during the clinical investigation, a subject must be prematurely withdrawn, the procedures outlined in this section must be followed. These procedures should not interfere with the initiation of any new treatments that are necessary to treat a subject's condition. Information on all withdrawn subjects will be documented.

Subjects may be withdrawn from the clinical investigation for any of the following reasons:

- a. Subject Withdrawal: A subject may voluntarily withdraw from the clinical investigation at any time and for any reason. The subject should be asked when possible, and without any form of coercion, the reason for his/her decision. If the participant withdraws from the clinical investigation completely, then data collected up until the point of withdrawal will be included in the final analysis. Subjects who decline to continue to take part will be given the opportunity to discuss/inform the research team of the reasoning behind their decision not to take part.
- b. Lost to Follow-Up (LTFU): A subject will be considered LTFU after all reasonable efforts have been made to contact the subject and request his/her continued participation in the clinical investigation. All attempts to contact the subject must be documented and should include at least two attempts to contact the subject by phone and one attempt via a certified letter. Data collected up until the point where the subject is LTFU will be included in the final analysis.

- c. Amputation: The discontinuation of a subject's participation in the clinical investigation due to Amputation (below the knee or above the knee) All available information concerning the amputation AEs should be provided. Data collected up until the point of amputation will be included in the final analysis.
- d. Adverse Event: The discontinuation of a subject's participation due to an AEs that prohibits his/her continued participation must be fully explained. All available information concerning the AEs should be provided. Data collected up until the point of AE will be included in the final analysis.

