## 11 Statistical Considerations

In general, the statistical analysis of will consider the combined outcome of all the devices under investigation. The population of the study will consist of all patients implanted with one or more of the devices listed Table 6.1. Subgroup analysis will be conducted for each device and device groups (i.e., devices for internal fixation only). The study required a sample size of 141 patients to provide at least 80% statistical power to reject the hypothesis that the 3-year amputation rate is less than the PG with a significance  $\alpha=0.05$ . The final statistical analysis will occur after all subjects have completed their 3-year anniversary. Secondary effectiveness endpoints include the total and component scores of the EQ-5D-5L and FAAM. Assessment of patient-reported outcome measure (PROM) improvement will be assessed at each planned study visit. The safety endpoints will include AEs, complications and secondary surgical intervention experienced by the patients. The device- and procedure- relatedness and severity of the safety endpoints will be assessed. The clinical and radiographic surgeon assessment of fusion and consolidation at 5 years will also be assessed.

Data will be captured via the EDC system. The data will be summarized descriptively at each pre-determined clinical visit. Quantitative factors will be summarized with mean, median, standard deviation and range minimum, maximum. Frequency and percentage will be computed for categorical factors. Survival analysis will be conducted to analyze time-to-event variables. Subjects without events will be censored at their last known event-free time point. Survival curves will be constructed using Kaplan-Meier estimates with confidence limits. A significance level ( $\alpha$ ) is 0.05 will be used for all tests of hypotheses

All statistical analysis will be performed using SAS version 9.4 or higher. A Statistical Analysis Plan (SAP) that contain the details of the analysis will be developed and finalized prior to the first anniversary of the first patient enrolled in the study.

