### 11.1 DETERMINATION OF SAMPLE SIZE

The sample size was determined by assuming a binomial distribution for the outcome of amputation to 3 years post treatment and then applying an adjustment for the maximum expected loss-to-follow-up. Based on preliminary data collected via retrospective studies that is on file with Stryker, the expected pooled amputation rate at 3 years for subjects meeting inclusion and exclusion criteria for this study is 10%.

An unadjusted chi-square test based on a 1-sided type 1 error rate of  $\alpha=0.025$  has 92% power to reject the null hypothesis that  $\pi_{amp} \geq 0.202$  in favor of the alternative hypothesis  $\pi_{amp} < 0.202$  (nQuery Advisor 7.0) with N=141 subjects. This sample size is increased by 29.5% to N=200 for account for loss-to-follow-up.

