#### 11.2.2 Primary Analysis / Endpoint

The primary effectiveness hypothesis will be tested on the basis of a confidence interval derived from a Kaplan-Meier analysis of cumulative amputation rates over time. The null and alternative hypotheses to be tested are as follows:

$H_0: \pi_{amp} \geq PG$  vs  $H_a: \pi_{amp} < PG$

$\pi_{amp}$  is the pooled 3-year cumulative rate of amputations, A Kaplan Meier survival estimate with confidence limits of the PG will be constructed for the time to amputation. These hypotheses will be tested by comparing the upper bound (UB) of a 1-sided 97.5% confidence interval (CI) at the 3-year to the target performance (PG). The null hypothesis ( $H_0$ ) will be rejected If  $UB < PG$ , and it will be concluded that the performance of the device(s) achieved the PG. This is approximately equivalent to specifying a 1-sided type 1 error rate of  $\alpha=0.025$ . A 1-sided type 1 error rate of  $\alpha=0.025$  rather than  $\alpha=0.05$  is specified to increase the robustness of the statistical evidence. A chart to depict the survival function with confidence limits will be presented.

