#### 11.2.4 Safety Analysis

All subjects enrolled in the study will be assessed for safety. AEs and other safety evaluations will be reported as frequencies and rates as appropriate, cumulative over the different follow-up schedules.

Safety endpoints will include all AEs, serious AE (SAE), device related adverse effect (DRAE), procedure related adverse effect (PRAE), serious device-related adverse effect (SDRAE), serious procedure-related adverse effect (SPRAE), unanticipated adverse device effects (UADEs) and type of surgical intervention as a consequence of the AE occurrence. For each type of AE and intervention type, total counts and per subject incident rates with 95% exact binomial confidence intervals will be reported. Counts of AE's will also be reported according to incidence time intervals.

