#### 11.2.5 Additional Analysis

There are two types of fixation, external and internal. External fixation devices are always removed. Survival analysis of time to external fixation removal with Kaplan-Meier survival estimates and corresponding confidence limits will be presented. Internal fixation breakage will be reported as an AE.

Subgroup analysis of patient reported outcome improvement scores (EQ-5D-5L and FAAM) will be conducted for i.) patients with external fixation only, ii.) patients with internal fixation only, iii.) patients with external and/or internal fixation. In addition, subgroup analysis will be conducted by device type (HOFFMANN® LRF SYSTEM, SALVATION™ EXTERNAL FIXATION SYSTEM, SALVATION™ FUSION BOLTS AND BEAMS, SALVATION™ 2 MIDFOOT NAIL, THE SALVATION™ 3DI PLATING SYSTEM, T2® ICF SYSTEM, and VALOR™ ANKLE FUSION NAIL).

**MISSING DATA** For the primary endpoint analysis, subjects that have not experienced the event (i.e., amputation) at the last day of follow-up will be censored in the survival analysis. Patients that dropped out for any reason before their 3-year anniversary will also be censored at the last known date. A sensitivity analysis will be conducted that will exclude patients that dropped out from the study for reasons other than amputation prior to their three-year anniversary.

For the patient reported outcomes (EQ-5D and FAAM), statistical summaries will be computed only for available data. No imputation for missing data will be conducted.

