9.1 Primary Effectiveness/Performance Analysis

None of the subjects reached their three-year post-surgery follow-up. Thus, the three-year amputation rate, which is the primary endpoint will not be analyzed. Instead, the frequency of amputations at each post-surgery visit will be presented. The status of the subject at the latest follow-up, coded as either walking, use of mobility aids, bedridden or having amputation will be summarized instead.

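### SAP 9.1 drops the censored time-to-amputation analysis for a reason that rules out only the 3-year rate, leaving no pooled amputation estimate with an interval; SAP 12 wrongly reports no changes

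*SAP*

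**What the plan says.** **Protocol.** The primary analysis (11.2.2) is a pooled Kaplan-Meier estimate of time to amputation, judged at 3 years against the performance goal, and "A chart to depict the survival function with confidence limits will be presented". Section 11 sets the censoring rule: "Subjects without events will be censored at their last known event-free time point". The missing-data text in 11.2.5 repeats it for the primary endpoint: "subjects that have not experienced the event (i.e., amputation) at the last day of follow-up will be censored in the survival analysis". Section 6 adds curves by device: "Descriptive analyses will then compare survival curves in patients for specific devices over the entire 5-year follow-up period". For safety, 11.2.4 states: "For each type of AE and intervention type, total counts and per subject incident rates with 95% exact binomial confidence intervals will be reported". Section 14 counts amputation among reoperations, and 9.4 makes it a reason for a subject's participation to end.

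**SAP.** Section 4.1 reports that enrolment stopped on 28 October 2022 with about 42 subjects implanted. Section 7 makes all analysis descriptive and excludes hypothesis tests. Section 9.1 gives the absence of 3-year follow-up as the reason for not analysing the primary endpoint, then says: "Instead, the frequency of amputations at each post-surgery visit will be presented". It adds each subject's status at latest follow-up. Section 6.5 takes the visit from the label on the form, without windowing. Section 14.1 lists no amputation table and 14.3 plans no figures. Kaplan-Meier appears only in the abbreviation list. Section 12 declares no change from the protocol's planned analysis.

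**The concern.** Amputation is the primary endpoint, and the protocol's method for it was built for incomplete follow-up. Early termination makes follow-up shorter and more uneven, which is when censoring and an interval are most useful. Yet the SAP keeps confidence intervals for patient-reported and radiographic means and plans none for amputation.

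The visit frequencies are hard to read as risks. The 1 Year window is plus or minus 6 months, and latest follow-up is a different time for each subject. Because amputation can end participation, a count among those attending a visit can miss subjects who lost the limb earlier, unless the count is cumulative.

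A bare zero, or one event in 42, could be over-read as evidence of good performance. A reader relying on SAP 12 would also not learn that the primary analysis was replaced.

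**Working it through.** **1. What the stated reason supports.** The planning figures are: null rate 0.202, expected rate 0.10 (protocol 11.1: "the expected pooled amputation rate at 3 years for subjects meeting inclusion and exclusion criteria for this study is 10" percent), one-sided alpha 0.025, N = 141. The normal-approximation power is

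Phi{[(0.202 − 0.10) − 1.96 × sqrt(0.202 × 0.798/141)] / sqrt(0.10 × 0.90/141)} = Phi(0.0357/0.0253) = 92.1%.

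This reproduces the stated 92%. With n = 42 the same formula gives Phi(−0.0194/0.0463), about 34%, even if all 42 had full 3-year follow-up. Dropping the test is sound, and a 3-year Kaplan-Meier estimate cannot be had when nobody is followed that long. Neither fact bears on an estimate at an earlier time.

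**2. What the remaining outputs give.**

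| Output | Pooled | Defined time | Interval |
|---|---|---|---|
| Frequency per visit (9.1) | not stated | no, visits not windowed | no |
| Latest status (9.1) | not stated | no | no |
| Table 3.3, Amputation row, N and % | no; blocks for four devices | 1 Year and Final visit labels | no |
| Table 1.3, cumulative failures | no, by device | Pre-op, 1 Year and Final visit labels | no |
| Adverse event listing and serious event narratives | individual cases | event timing in narratives | no |

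Table 3.3 has no block for the Salvation external fixation, Hoffmann LRF or T2 ICF systems, and no 6-month column, although 9.1 promises every post-surgery visit.

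**3. What an exact interval would show.** The Clopper-Pearson upper limit for k events in n = 42 is the 0.975 quantile of Beta(k + 1, 42 − k). For k = 0 this is 1 − 0.025^(1/42) = 8.4%.

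| Events | Proportion | Exact 95% CI |
|---|---|---|
| 0 | 0% | 0 to 8.4% |
| 1 | 2.4% | 0.1 to 12.6% |
| 2 | 4.8% | 0.6 to 16.2% |

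**4. What a Kaplan-Meier estimate would add.** The documents do not give follow-up lengths, so this is an illustration. Assume the protocol's 10% at 3 years, a constant hazard λ = −ln(0.90)/36 = 0.002927 per month, 42 subjects, and independent censoring, uniform over the months shown. The true risk is 1 − 0.9^(6/36) = 1.74% at 6 months and 1 − 0.9^(12/36) = 3.45% at 12. The expected value of observed events/42 by month t is the integral from 0 to t of λ exp(−λu) G(u) du, where G(u) is the probability of still being followed at u. Taken over all follow-up, this integral is p; expected events are 42p and the chance of none is (1 − p)^42. The expected number at risk at 12 months is 42 exp(−12λ) G(12).

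| Censoring (months) | Events/42 at 6 mo | Events/42 at 12 mo | At risk at 12 mo | Expected events | Chance of none |
|---|---|---|---|---|---|
| 0–18 | 1.45% | 2.3% | 13.5 | 1.09 | 33% |
| 6–18 | 1.74% | 3.0% | 20.3 | 1.45 | 23% |
| 3–24 | 1.68% | 2.9% | 23.2 | 1.62 | 19% |
| 0–12 | 1.31% | not supported | 0 | 0.73 | 48% |

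In simulation under the first three patterns, Kaplan-Meier averages 1.73–1.75% at 6 months and about 3.45% at 12, so it removes the understatement. The understatement at 6 months is at most 1.74 − 1.31, about 0.4 points. Root mean squared error at 6 months is 2.2, 2.0 and 2.1 points for Kaplan-Meier against 1.9, 2.0 and 2.0 for events/42. At 12 months it is about 3.7, 3.1 and 3.1 against 2.6, 2.7 and 2.6. Censoring deaths at an assumed 5% or 10% yearly mortality shifts the 12-month figure by under 0.2 points (3.45% against a cumulative incidence of 3.36% or 3.28%).

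**The case against.** The best case for the SAP is that little can be learned from one or two events. No hypothesis is tested, the performance-goal comparison is gone, and SAP 7 gives early termination as the ground for describing only. Categorical data are promised as frequency and percent (SAP 8), Table 3.3 shows amputations with N and %, and one subject set is named (SAP 7.2). Narratives and listings would let a reader recover each amputation reported as a serious event. The protocol never specified a 6- or 12-month amputation estimate, and its section 6 curves are by device. Follow-up may also be short: protocol version 1 is dated 7 October 2021, under 13 months before enrolment stopped. Subjects may have been followed after that date, so this is not certain.

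Most of this stands, and it limits the point. A reader might infer that the SAP will present events/42 as a 12-month risk, and so a biased primary result. It does not say so: the denominator in 9.1 is not spelled out and no such risk is claimed. Nor is it right that amputation goes unreported, given Table 3.3. A reader might also infer that Kaplan-Meier would be the more accurate estimate; the errors above show that it is not.

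What the objection does not answer is that the stated reason removes more than it justifies, that no pooled interval is left, and that SAP 12 is incorrect.

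**Conclusion.** The point holds as a cheap improvement, together with one plain error. SAP 12 is wrong as written: 9.1 replaces the primary analysis, 7 removes hypothesis testing and 7.3 removes the planned subgroup analyses.

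The absence of 3-year follow-up justifies dropping the 3-year rate and the test. It does not justify dropping every censored or interval summary of amputation. The practical loss is the interval: upper limits of 8.4% to 16.2% for 0 to 2 events in 42 are what keep a low count from being over-read.

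The case for Kaplan-Meier is weaker. Its gain is at 12 months (3.45% against 2.3–3.0%) and is small at 6. It depends on follow-up that the documents do not give, on a constant hazard, and on censoring unrelated to amputation risk. With follow-up of 0–12 months there would be no 12-month estimate, and about 48% of such trials would have no event. It belongs beside the counts, not in their place.

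The documents do not support asking for the 3-year rate or the performance-goal comparison to be restored.

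**What to change.** 1. In SAP 9.1, report the pooled cumulative number of subjects with above- or below-knee amputation among all implanted subjects (the SAP 7.2 set), with an exact 95% CI and total person-time. Protocol 11.2.4 already planned exact binomial intervals for intervention types.
2. As a supplement, give one pooled descriptive Kaplan-Meier estimate from index surgery, censored at the last known event-free date, with number at risk and 95% CI at 6 months. Add 12 months only if the number at risk meets a threshold written into the SAP before the data are tabulated. Make no performance-goal test.
3. Make the visit counts cumulative and add a pooled row to Table 3.3.
4. Correct SAP 12 to list the departures from the protocol and their reasons.

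The cost is one procedure, one extra table and some text. No figure is needed, and the protocol's analysis already required the amputation and last event-free dates. The drawback is imprecision: with about 0.7 to 1.6 expected events the Kaplan-Meier interval will be wide, and the report should say so.

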6.3 Withdrawal / Follow-up

The study allowed subjects to withdraw from the clinical investigation for any of the following reasons:

- a. Voluntary withdrawal by the subject;
- b. Subject was Lost to Follow-Up (LTFU);
- c. Amputation below the knee or above the knee;
- d. Adverse event that prohibited the subject from continued participation;
- e. Subject non-compliance to study protocol; and
- f. Other reason(s) that may have exposed the subject to unacceptable risk.

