8.5 Operative Variables

The following surgical information will be summarized: indication for implant use, operative side (left or right), previous surgery to index procedure, biologics use, and intraoperative complications.

9 Summary of Effectiveness/Performance Data

EuroQol (EQ-5D-5L)

A generic health survey can be used to compare improvement across different interventions and measure changes in health-related quality of life over time. The EQ-5D-5L comprises 5 dimensions: mobility, self-care, usual activities, pain/discomfort, anxiety/depression. Each dimension has five levels: no problems, slight problems, moderate problems, severe problems, and 100 on VAS indicates the best health, whereas 0 on the VAS indicates the worst health. Patient health profiles with concerning mobility, self-care, activities, pain/discomfort and anxiety/depression will be presented as frequency and rates. In addition, the summaries for improvement from baseline in VAS health score will be presented. Also, summaries for the converted EQ-5D-5L index value will be presented. At each post-surgery follow-up visit, descriptive statistics and confidence interval estimates of the mean will be constructed for the change in scores.

FAAM

The Foot and Ankle Ability Measure (FAAM) is a self-report outcome instrument to assess physical function for individuals with foot and ankle-related impairments. The FAAM consists of 29-item questions divided into two subscales: 21-item activities of daily living (ADL) subscale, an 8-item sports subscale. Each item is scored on a 5-point Likert scale (4 to 0) from 'no difficulty at all' to 'unable to do'. Responses of "not applicable" are not counted. The scores of the sub-scale items will be added together to get the subscale total score. The ADL subscale total score ranges from 0 to 84, and 0 to 32 for the sports subscale. The patient score for the ADL and sports subscale will be transformed into percentage scores by considering the highest possible score for non-missing items. A higher score indicates a higher level of function for each subscale, with 100% representing no dysfunction (Martin et al., 2009).

Surgeon Assessment and radiographic outcome

The attending surgeon assessed the outcome of the implant one year after surgery and at the final visit. The following factors were assessed by the surgeon:

- Insulin use
- Ulcer healing and presence of new ulcers
- Presence of new deep infection
- Ankle alignment status

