15.1 All Table Shells

Table 1.1 Subject Disposition – ITT

Device	Pre-Op	Final F-up (Op- 1yr)	Post-Op (1 yr.)
SALVATION™ 3Di Plating			
Total			
Available Data			
Reason for Discontinuation			
Subject lost to follow-up			
Subject withdrew consent			
Adverse Event			
Other			
SALVATION™ External Fixation			
Total			
Available Data			
Reason for Discontinuation			
Subject lost to follow-up			
Subject withdrew consent			
Adverse Event			
Other			
SALVATION™ Fusion Bolts and Beams			
Total			
Available Data			
Reason for Discontinuation			
Subject lost to follow-up			
Subject withdrew consent			
Adverse Event			
Other			
SALVATION™ MIDFOOT NAIL			
Total			
Available Data			
Reason for Discontinuation			
Subject lost to follow-up			
Subject withdrew consent			
Adverse Event			
Other			

Device	Pre-Op	Final F-up (Op- 1yr)	Post-Op (1 yr.)
VALOR™ Nail			
Total			
Available Data			
Reason for Discontinuation			
Subject lost to follow-up			
Subject withdrew consent			
Adverse Event			
Other			
HOFFMANN® LRF SYSTEM			
Total			
Available Data			
Reason for Discontinuation			
Subject lost to follow-up			
Subject withdrew consent			
Adverse Event			
Other			
T2® ICF SYSTEM			
Total			
Available Data			
Reason for Discontinuation			
Subject lost to follow-up			
Subject withdrew consent			
Adverse Event			
Other			

Table 1.2 Subject Eligibility

Table 1.3 Subject Accounting and Follow-up Compliance – ITT

Device	Pre-op	1 Year	Final Visit
	N	N	N
SALVATION™ 3Di Plating System			
Theoretical			
Deaths (cumulative)			
Failures (cumulative)			
Withdrawn (cumulative)			
Expected			
Actual ¹			
% Follow-up ¹			
EQ-5D Score			
FAAM Score			
SALVATION™ External Fixation			
Theoretical			
Deaths (cumulative)			
Failures (cumulative)			
Withdrawn (cumulative)			
Expected			
Actual ¹			
% Follow-up ¹			
EQ-5D Score			
FAAM Score			
SALVATION™ Fusion Bolts and Beams			
Theoretical			
Deaths (cumulative)			
Failures (cumulative)			
Withdrawn (cumulative)			
Expected			
Actual ¹			
% Follow-up ¹			
EQ-5D Score			
FAAM Score			
SALVATION™ MIDFOOT NAIL			
Theoretical			
Deaths (cumulative)			
Failures (cumulative)			
Withdrawn (cumulative)			
Expected			
Actual ¹			
% Follow-up ¹			
EQ-5D Score			
FAAM Score			
VALOR™ Nail			
Theoretical			
Deaths (cumulative)			
Failures (cumulative)			

Withdrawn (cumulative)			
Expected			
Actual ¹			
% Follow-up ¹			
EQ-5D Score			
FAAM Score			
¹Any data point available at follow-up			

Table 1.4 CIP Deviations

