ADL Subscale					xx	xx.x ± xx.x	xx.x , xx.x	xx.x, xx.x	xx	xx.x ± xx.x	xx.x , xx.x	xx.x, xx.x

	Baseline				Final Visit				1 Yr. Visit			
	n	Mean ± SD	min,max	95% CI	n	Mean ± SD	min,max	95% CI	n	Mean ± SD	min,max	95% CI
Sports Subscale	xx	xx.x ± xx.x	xx.x, xx.x	xx.x, xx.x	xx	xx.x, xx.x	xx.x, xx.x	xx.x, xx.x	xx	xx.x ± xx.x	xx.x, xx.x	xx.x, xx.x
ADL Subscale	xx	xx.x ± xx.x	xx.x, xx.x	xx.x, xx.x	xx	xx.x, xx.x	xx.x, xx.x	xx.x, xx.x	xx	xx.x ± xx.x	xx.x, xx.x	xx.x, xx.x
SALVATION™ External Fixation												
FAAM SANE	xx	xx.x ± xx.x	xx.x, xx.x	xx.x, xx.x	xx	xx.x ± xx.x	xx.x, xx.x	xx.x, xx.x	xx	xx.x ± xx.x	xx.x, xx.x	xx.x, xx.x
Sports Subscale	xx	xx.x ± xx.x	xx.x, xx.x	xx.x, xx.x	xx	xx.x ± xx.x	xx.x, xx.x	xx.x, xx.x	xx	xx.x ± xx.x	xx.x, xx.x	xx.x, xx.x
ADL Subscale	xx	xx.x ± xx.x	xx.x, xx.x	xx.x, xx.x	xx	xx.x ± xx.x	xx.x, xx.x	xx.x, xx.x	xx	xx.x ± xx.x	xx.x, xx.x	xx.x, xx.x
Change from Baseline												
FAAM SANE					xx	xx.x ± xx.x	xx.x, xx.x	xx.x, xx.x	xx	xx.x ± xx.x	xx.x, xx.x	xx.x, xx.x
Sports Subscale					xx	xx.x ± xx.x	xx.x, xx.x	xx.x, xx.x	xx	xx.x ± xx.x	xx.x, xx.x	xx.x, xx.x
ADL Subscale					xx	xx.x ± xx.x	xx.x, xx.x	xx.x, xx.x	xx	xx.x ± xx.x	xx.x, xx.x	xx.x, xx.x

SANE -Single Assessment Numeric Evaluation.

Table 3.3 Surgeon Assessment

Device	Factors	1 Year Visit		Final Visit	
		N	%	N	%
SALVATION™ Fusion Bolts and Beams	Insulin Use				
	Yes	xx	xx.x%		
	No	xx	xx.x%		
	Ulcers	New Ulcer		Ulcer Healing	
	Yes	xx	xx.x%	xx	xx.x%
	No	xx	xx.x%	xx	xx.x%
	Chronic Ulcer				
	Yes	xx	xx.x%		
	No	xx	xx.x%		
	New Deep Infection				
	Yes	xx	xx.x%		
	No	xx	xx.x%		
	Ankle Alignment				
	Acceptable			xx	xx.x%
	Unacceptable			xx	xx.x%
	Not applicable			xx	xx.x%
	Current Status				
	Walking	xx	xx.x%	xx	xx.x%
	Mobility with aids	xx	xx.x%	xx	xx.x%
	Wheelchair	xx	xx.x%	xx	xx.x%
	Bed ridden	xx	xx.x%	xx	xx.x%
	Amputation	xx	xx.x%	xx	xx.x%
SALVATION™ Midfoot Nail	Insulin Use				
	Yes	xx	xx.x%		
	No	xx	xx.x%		
	Ulcers	New Ulcer		Ulcer Healing	
	Yes	xx	xx.x%	xx	xx.x%
	No	xx	xx.x%	xx	xx.x%
	Chronic Ulcer				
	Yes	xx	xx.x%		
	No	xx	xx.x%		
	New Deep Infection				
	Yes	xx	xx.x%		
	No	xx	xx.x%		
	Ankle Alignment				
	Acceptable			xx	xx.x%
	Unacceptable			xx	xx.x%
	Not applicable			xx	xx.x%
	Current Status				
	Walking	xx	xx.x%	xx	xx.x%
	Mobility with aids	xx	xx.x%	xx	xx.x%

Device	Factors	1 Year Visit		Final Visit	
		N	%	N	%
	Wheelchair	xx	xx.x%	xx	xx.x%
	Bed ridden	xx	xx.x%	xx	xx.x%
	Amputation	xx	xx.x%	xx	xx.x%
SALVATION™ 3Di Plating System	Insulin Use				
	Yes	xx	xx.x%		

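### SAP 9.1 reduces the primary outcome to visit-based amputation summaries with no named source or denominator, so a subject who leaves at amputation can be missed or shown at an earlier status

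*SAP*

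**What the plan says.** SAP 9.1 states that the 3-year rate will not be analysed and gives two substitutes. The first is a count by visit: "Instead, the frequency of amputations at each post-surgery visit will be presented". The second is "The status of the subject at the latest follow-up, coded as either walking, use of mobility aids, bedridden or having amputation". The section does not say which form supplies either summary, what the denominator is, or how an amputation between two visits is handled.

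On when status is recorded, the surgeon-assessment text in SAP section 9 says: "The attending surgeon assessed the outcome of the implant one year after surgery and at the final visit". Table 3.3 in SAP 15.1 follows this. Its "Current Status" block has an Amputation row, with columns for the 1 Year Visit and the Final Visit.

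Both documents list amputation among the reasons for leaving the study. SAP 6.3(c) has "Amputation below the knee or above the knee". Protocol 9.4(c) adds: "Data collected up until the point of amputation will be included in the final analysis". Under "Reason for Discontinuation", Table 1.1 offers loss to follow-up, withdrawn consent, adverse event and other. It has no amputation category.

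**The concern.** Amputation is the primary outcome, and these two summaries are what is left of it. In a count built on visits, the event being counted can itself be the reason that the next visit does not happen. Amputees are then the subjects most likely to have no later form. The error runs one way: a missed amputee always makes the devices look better. In a study of about 42 subjects with few expected events, one or two missed amputees change the picture noticeably. In addition, two programmers working from the present text could report different amputation counts from the same database.

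**Working it through.** The plan gives no amputation count, so there is no figure of its own to reproduce on this point. The planned sample size and power do not bear on it. The check sets the rules side by side and then sizes the effect under stated assumptions.

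**1. Event-based analysis against visit-based summary.** Protocol 11.2.2 planned a Kaplan-Meier analysis of time to amputation. There the amputation is a dated event, so leaving the study at that moment does no harm. The missing-data paragraph of protocol 11.2.5 plans a sensitivity analysis that removes dropouts other than those due to amputation, so the protocol itself treats amputation as a form of exit. The difficulty arises only when SAP 9.1 moves from the event to the visit.

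**2. One subject followed through the rules.** Suppose a subject is recorded as walking at month 6, is amputated at month 8 and leaves.
- SAP 6.5 assigns visits from the form completed, and SAP 7.5 imputes nothing.
- With no 1-year form, the subject is not in the 1-year percentage.
- If no final assessment is completed at exit, the last status on file is walking.

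**3. Can the other specified outputs recover the event?**
- Table 1.1 would place it under adverse event or other.
- Table 4.1 shows only surgery as a required treatment.
- Protocol section 14 collects amputation as a reoperation, but SAP 14.1 and 14.2 list no table or listing of reoperations or surgical interventions.
- Table 3.3 has blocks for four systems only (Fusion Bolts and Beams, Midfoot Nail, 3Di Plating, VALOR Nail). An amputee treated only with Salvation External Fixation, Hoffmann LRF or T2 ICF has no row there.

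**4. Size.** Inputs:
- about 42 implanted subjects (SAP 4.1);
- an expected 3-year rate of 10% (protocol 11.1);
- a literature figure of 17.2% at a mean of 29.5 months (protocol section 8).

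The number of amputees and the number missed are assumptions.

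Plausible number of events, assuming a constant hazard and one year of follow-up for all 42, and reading the 17.2% as the cumulative risk at 29.5 months:
- from 10% at 3 years: 1 − 0.90^(1/3) = 3.45%; × 42 = 1.4;
- from 17.2% at 29.5 months: 1 − 0.828^(12/29.5) = 7.39%; × 42 = 3.1.

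Let t be the true number of amputees and m the number missed, with everyone else assessed. If missed amputees are carried at an earlier status, the reported proportion is (t − m)/42. If they drop out of the denominator, it is (t − m)/(42 − m).

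| t | True proportion | One missed, carried | One missed, dropped | All missed |
|---|---|---|---|---|
| 2 | 2/42 = 4.8% | 1/42 = 2.4% | 1/41 = 2.4% | 0% |
| 3 | 3/42 = 7.1% | 2/42 = 4.8% | 2/41 = 4.9% | 0% |
| 4 | 4/42 = 9.5% | 3/42 = 7.1% | 3/41 = 7.3% | 0% |

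The loss from one missed subject is 1/42 = 2.38 points if carried. If dropped, it is 4.76 − 2.44 = 2.32 points (t = 2), 7.14 − 4.88 = 2.26 (t = 3) or 9.52 − 7.32 = 2.21 (t = 4, from unrounded values). That gives about 2.2 to 2.4 points. With t = 7 the dropped version costs a little less: 16.67 − 14.63 = 2.03 points.

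For scale, 3 of 42 has an exact 95% confidence interval of 1.5% to 19.5%. With one missed, 2 of 42 has 0.6% to 16.2%. With all three missed, 0 of 42 has 0% to 8.4%.

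**The case against.** A reader might infer that the plan removes every subject at amputation and that the SAP's count must therefore lose them. The documents do not support that, for four reasons.

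- **Withdrawal is permitted, not required.** Protocol 9.4 says that subjects may be withdrawn for the listed reasons, and SAP 6.3 says that the study allowed it. Protocol 9.4(c) also asks for all available information on the amputation, and wording similar to its data sentence is used for other exits. It does not order the event itself to be discarded.
- **The source of the by-visit count is unstated.** It is not shown to exclude other records. Adverse event or surgical-intervention records grouped by visit would fit the text equally well, and protocol 11.2.4 plans adverse event counts by time interval.
- **An exit assessment may exist.** Table 1.1 has a final follow-up column covering operation to one year, and the Amputation row under Final Visit in Table 3.3 suggests that some amputees were expected to be recorded there. Disposition is completed at any withdrawal.
- **Other outputs may show the event.** Table 1.3 has a cumulative failures row, although failure is not defined. A major amputation would ordinarily meet the SAE definition, so a narrative under SAP 10.2 and an entry in Listing 12 are likely. The layouts of Tables 4.2 and 4.3 could not be seen and are not counted against the plan.

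These points stand, and they limit the finding to what can happen under the present wording. They do not remove it. SAP 9.1 invokes none of these safeguards, and an event that appears in a narrative does not correct a summary percentage that left it out.

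**Conclusion.** The point holds as a gap in definition with a one-directional risk. SAP 9.1 names no source or denominator, and the only readable shell with an Amputation row depends on two surgeon assessments. Exit at amputation is allowed. An amputee without a final assessment at exit can therefore be absent from a later-visit percentage or appear at a pre-amputation status.

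Each such loss lowers the reported figure by about 2.2 to 2.4 percentage points. This assumes 42 subjects, two to four true amputees and everyone else assessed. These are illustrations: the documents give no amputation count, no follow-up distribution and no number of exits without a final form. They do not show that any amputation has been or will be lost.

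It should be fixed, because this is what remains of the primary outcome and the repair is cheap. It is not more serious than that. SAP section 7 makes the analysis descriptive only, no hypothesis is tested, and no decision rule depends on the figure.

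**What to change.** In SAP 9.1:
- Report the cumulative number of subjects ever amputated (above or below the knee), with the date, drawn from the adverse event, Surgical Intervention, Subject Disposition and visit-assessment records. Use all implanted subjects as the denominator.
- State that amputation overrides any earlier status at latest follow-up.
- State that amputees stay in both the count and the denominator at later visits, whether or not a visit took place.

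In the shells, add Amputation as a reason in Table 1.1, and reconcile its count with Table 3.3 and the adverse event listing.

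The withdrawal rule itself need not change. The cost is some SAP wording and one derived variable from forms already in the schedule, with no new data. The reported figure may be slightly less favourable.
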